### 9.4 Intensive PK study

#### 9.4.1 Sample Size

Using measures of mean AUC and its coefficients of variation (CV) from our studies and the literature, the intensive arms of the study are powered to detect differences in ACT AUC between all study groups (3-day AL vs 5-day AL) with  $n=30$  for each group of HIV infected children. To assure adequate age-matched HIV uninfected children,  $n=50$  is used for the group of HIV uninfected children. Figure 1 and Table 8. 50 HIV-uninfected children provides for adequate subjects  $< 3$  years and  $\geq 3$  years of age as HIV-infected children receiving EFV-based ART is restricted to  $\geq 3$  years of age. In addition, the same size of 50 will permit PK/PD of the extended regimen in younger children  $< 3$  years of age. At least 30 HIV uninfected children must be between 3-10 years of age.

For comparisons where  $n=30$  in both groups, there will be 80% power to detect a difference in AUC of 35% or more, given an overall Type I error of 0.05, a Bonferroni correction for multiple comparisons, and with assumption that the coefficient of variation (CV) for all AUC's is 35-38%. For the HIV-uninfected children with  $n=50$ , further distinctions based on age can be determined as well as further enhancement of exposure-response analysis.

Although many children are likely to be studied for both the 3-day and 5-day regimens, it is not likely that *all* children will provide results for both. However, all analyses will account for repeated measures/correlated data that occur from participants enrolled into multiple arms.

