**1.1.3 Malaria and HIV in Uganda.** Uganda bears a heavy burden of both malaria and HIV. Although malaria prevention and control programs have reduced infections and mortality overall, Uganda still has one of the highest malaria transmission intensities in the world. In Tororo, the site of this proposal, children experience up to 2 to 6 malaria episodes per year, despite usage of bed nets and trimethoprim-sulfamethoxazole (TS) for those HIV-infected. For HIV, Uganda is lauded for prior success in stemming the HIV epidemic, but new infections are now on the rise. It is estimated that 2 million HIV-infected children will reside in sub-Saharan Africa in 2020. Thus, HIV-malaria co-infection remains common, with treatment complicated by multiple pharmacological factors that require field-based studies, such as those currently proposed in this renewal.

**1.1.4 Significant drug interactions occur between ART and ACT.** Both components of AL are extensively metabolized. Artemether undergoes rapid demethylation by cytochrome p450 3A4 (CYP3A4) and CYP2B6 to the active metabolite,

dihydroartemisinin (DHA), which undergoes further metabolism via UDP-glucuronosyltransferases (UGT). CYP3A4 is also responsible for metabolizing lumefantrine to desbutyl-lumefantrine (desbutyl-LR), and was shown by our group to be

Table 1	Comparison of AL PK exposure in HIV-infected children on ART compared to HIV-uninfected children (controls)		
	HIV-uninfected	HIV-infected	
	AL alone (control)	AL+EFV	
	GM; 95%CI (n=52)	GM; 95%CI (n=31)	GMR, EFV/Control
AR_AUC 0-8	120 (97.6-147) a	48.5 (37.2, 63.1)	0.40***
DHA_AUC 0-8	212 (176, 256) a	62.9 (49.2, 80.3)	0.30***
LR_AUC 0-∞	270 (232, 313)	130 (107, 157)	0.48***
LR Half-life b	64.3 (52.0, 121)	23.7 (21.8, 46.0)	0.37***
Intensive and sparse PK (n=363 episodes)			
	Median (IQR), n=186	Median (IQR), n=48	MR, EFV/Control
LR C 7d	340 (257, 531)	111 (63, 192)	0.30***
LR C 14d	86 (59, 137)	BLQ (BLQ,BLQ)	<1***
LR C 21d	BLQ (BLQ, 63)	BLQ (BLQ,BLQ)	<1**

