## 9.0 STATISTICAL CONSIDERATIONS

### 9.1 General Design Issues.

This is a prospective study to evaluate the PK and PD of extended dose AL in the context of EFV-based ART and in the context of HIV-uninfected children and to characterize the impact of a 5-day regimen on AL PK/PD as compared to the standard 3-day regimen; the study will be conducted in Uganda.

The current proposal will study the PK/PD of AL in HIV-infected children on EFV-based ART and HIV-uninfected children not on ART either enrolled at TDH or MGH. We will compare the PK of 5-day AL in HIV-infected children on EFV-based ART to 1) 3-day AL in HIV-infected children on EFV-based ART, and 2) 3-day AL in HIV-uninfected children. In addition, we will compare the PK of 5-day AL in HIV-uninfected children to 3-day AL in HIV-uninfected children. Comparisons will be based on an intensive PK design for AL AUC estimations in 30 to 50 subjects for each of the study groups. Study group comparisons will be controlled for age (i.e. results for HIV infected children on EFV-based ART who are 3-10 years of age, will be compared to results for HIV uninfected children who are also 3-10 years of age). The proposal will also study the impact of AL exposure on treatment outcomes and adverse events using a population PK/PD design. This will involve population PK study of up to an additional 100 HIV-infected children and 120 HIV-uninfected children.

*Although an individual child is eligible to enroll in both the intensive PK study and the population PK study for separate episodes of malaria, there is no assurance that the same child will contribute to both study components. Thus, it is possible that the total number of subjects for all groups may be as high as 380.*

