#### 9.4.2 Intensive PK Analysis

PK parameters for each subject will be estimated using non-compartmental analysis (NONCMP) and follow a linear up-log down trapezoidal rule in conjunction with first-order input (WinNonlin). PK parameters, including the elimination rate constant  $\lambda_z$  and  $t_{1/2}$  will be estimated, with  $t_{1/2}$  calculated as  $\ln_2/\lambda_z$ . AUC will be estimated as the  $AUC_{0-8h}$  or  $AUC_{0-24h}$  (as results permit) for artemether/DHA and the sum of  $AUC_{last}$  (AUC to the

end of the sampling period) and  $AUC_{last-\infty}$  (from the end of sampling to infinity) for lumefantrine/ desbutyl-lumefantrine. PK parameters will be compared between groups of interest (Figure 1 and Table 8) using a two-sided unpaired t-test for two-group comparisons, and ANOVA for multi-group comparisons. If PK parameters are found to have skewed distributions and data transformations do not induce symmetry, rank-based tests will be used. To enhance comparison between 3-day and 5-day AL, peak concentrations collected on Days 0-4 will be integrated using population methods. The following groups will be compared:

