## 9.5 Population PK study

### 9.5.1 Sample Size

160 episodes of malaria in HIV-infected children and 220 episodes of malaria in HIV-uninfected children (up to 4 episodes per child including up to 2 involving intensive sampling) are more than sufficient to obtain population PK parameter estimates for both groups of children with good precision. Outcomes will be assessed in children in both the intensive and population PK studies, as such, sample sizes reflect the sum of children enrolled in each arm for each type of PK sampling. Thus, total sample sizes will be 80 to 110 children per arm. Using WinPOPT®, the standard errors (SE) of all population PK parameters, including variability parameters, will be <20% of their means, except for the interindividual variability of  $k_a$ , for which the SE is estimated to be 32% of its mean. Based on our recent study from Tororo, where a 42-day recurrence rate of 47% was observed in those on EFV-based ART, we will have 80% power to detect a 20% difference in recurrence rates between 3-day and 5-day arms. Notably, in our previous exposure-outcomes, with 50 to 70 children in each ART arm and 184 children not on ART, a 2.1-fold change in AUC between those on EFV and lopinavir/ritonavir translated to a 2.7-fold increase in risk for reinfection. In other words, the anticipated increase in AUC between 5-day and 3-day AL of 1.7-fold increase in exposure is expected to translate to a clinically relevant change in risk in a similar number of subjects.

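### The 35–38% CV assumed for every AUC in Section 9.4.1 conflicts with the protocol's own Table 1 (about 56–58% for lumefantrine, 75% or more for DHA and artemether), so the stated 80% power is unsupported

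*Combined protocol and SAP*

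**What the plan says.** Section 9.2.1 makes AUC, for all drug analytes, the first primary outcome. Section 9.4.1 gives its only power statement, which applies where each arm has 30 children: "there will be 80% power to detect a difference in AUC of 35% or more, given an overall Type I error of 0.05", with a Bonferroni correction. It sets "the coefficient of variation (CV) for all" AUCs at 35–38%. The stated basis is the investigators' own studies and the literature, with no figures. The number of comparisons, the scale and the direction of the 35% are not given.

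Section 9.4.2 compares groups "using a two-sided unpaired t-test for two-group comparisons, and ANOVA for multi-group comparisons", with transformation or rank tests if distributions are skewed. Section 9.4.1 says that analyses will account for correlated data, and Section 9.1 adds: "Study group comparisons will be controlled for age". Section 9.5.1 refers to "the anticipated increase in AUC between 5-day and 3-day AL of 1.7-fold increase in exposure", without naming the analyte.

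Table 1 in Section 1.1.4 reports geometric mean AUCs with 95% confidence intervals for artemether, DHA and lumefantrine, in 31 children on efavirenz and 52 HIV-uninfected controls.

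**The concern.** The Table 1 intervals look too wide for a CV of 35–38% at the sample sizes shown. Table 1 is also close to the planned study: similar children, AUC0–8 for artemether and DHA, and AUC0–∞ for lumefantrine. If its variability applies, power for the stated difference is well under 80% for all three analytes.

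What is at stake is how the AUC comparisons are read. Section 9.4.1 does not discuss null results, but a reader who relied on it could take a non-significant 5-day versus 3-day comparison as evidence against a 35% difference. For artemether and DHA that inference would rest on power of about 20–26%.

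**Working it through.** **1. Reproduce the plan's figure.** Inputs: n=30 vs 30, two-sided unpaired t-test (58 df), CV 35–38%, alpha 0.05/3. The divisor of 3 is an assumption: Table 8 has three comparisons. On the log scale SD = √ln(1+CV²) and the effect is ln(1.35) = 0.300. Power comes from the noncentral t with noncentrality effect/(SD·√(2/30)).

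| CV | log-SD | Power, ratio 1.35 | Power, raw scale (0.35/CV) |
|---|---|---|---|
| 35% | 0.340 | 83% | 92% |
| 36% | 0.349 | 80% | 90% |
| 38% | 0.367 | 76% | 86% |

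So the 80% follows from the stated inputs. The question is the CV.

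**2. Variability implied by Table 1.** Log-SD = ln(upper/lower)·√n / (2·t₀.₉₇₅,ₙ₋₁); CV = √(exp(SD²)−1). The t quantile is 2.042 for n=31 and 2.008 for n=52. Example, lumefantrine on efavirenz: ln(157/107) = 0.383; 0.383 × √31 / (2 × 2.042) = 0.523; CV 56%. The 95% limits come from the chi-square limits of the log-SD.

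| Cell | GM (95% CI) | n | log-SD | CV | 95% limits of CV |
|---|---|---|---|---|---|
| Lumefantrine, EFV | 130 (107–157) | 31 | 0.523 | 56% | 44–79% |
| Lumefantrine, control | 270 (232–313) | 52 | 0.538 | 58% | 47–75% |
| DHA, EFV | 62.9 (49.2–80.3) | 31 | 0.668 | 75% | 57–110% |
| Artemether, EFV | 48.5 (37.2–63.1) | 31 | 0.720 | 82% | 63–124% |
| DHA, control (footnoted) | 212 (176–256) | 52 | 0.673 | 76% | not used |
| Artemether, control (footnoted) | 120 (97.6–147) | 52 | 0.736 | 85% | not used |

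The intervals are symmetric on the log scale (√(107×157) = 129.6 against a printed 130), so the back-calculation is appropriate. The footnote on the last two cells is not visible and might change their n, so the argument rests on the other four. All four have lower limits above 38%. For a CV of 35–38% to give the printed efavirenz intervals, n would have to be about 15–17 (lumefantrine), 10–11 (DHA) or 9–10 (artemether), not 31.

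**3. Power at n=30 vs 30 with the Table 1 values.**

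| Target difference | Alpha | Lumefantrine | DHA | Artemether |
|---|---|---|---|---|
| 35% increase or raw-scale difference | 0.05/3 | 39–49% | 24–26% | 20–22% |
| Same | 0.05 | 57–66% | 40–43% | 34–37% |
| 35% reduction (ratio 0.65) | 0.05/3 | 74–76% | 51–52% | 43–45% |
| Anticipated ratio 1.7 | 0.05/3 | 91–93% | 72–73% | 63–65% |

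**4. Largest CV that still gives 80% power** at alpha 0.05/3: 36% (ratio 1.35), 41% (raw scale), 54% (ratio 0.65). Every Table 1 point estimate is higher.

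**5. Could adjustment close the gap?** For ratio 1.35 the log-SD must be at most 0.350, so the share of variance to be removed is 1 − (0.350/SD)². That is 55–58% for lumefantrine, 72–73% for DHA and 76–77% for artemether.

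**6. What n=30 per group can detect** with 80% power at alpha 0.05/3: ratios of about 1.56–1.59 (lumefantrine), 1.77–1.78 (DHA) and 1.85–1.88 (artemether).

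**The case against.** The strongest reply is that this is a planning assumption, not a miscalculation, and that Section 9.4.1 does not say its CV came from Table 1. That is right: the arithmetic is sound and the sponsor may hold other data. But no such data are shown, and the protocol should not assume for all AUCs a CV that its own table excludes for every analyte.

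A second reply is that 35% may mean a reduction. Lumefantrine then has 74–76% power with a divisor of 3, 79–81% with 2 and 86–88% with none. The 54% CV ceiling for this reading also lies inside the confidence limits of both lumefantrine cells. So on this reading Table 1 does not clearly contradict the claim for lumefantrine. DHA and artemether still fall short, at 68–69% and 61–63% even uncorrected. The 5-day versus 3-day hypotheses are also about higher exposure.

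Third, some planned comparisons are well powered for larger effects. Table 8's second row, as printed, sets 3-day AL on efavirenz against 3-day AL in controls. At the Table 1 ratios of 0.48 (lumefantrine), 0.30 (DHA) and 0.40 (artemether), power is 99% or more. In the third row (n=50 per arm), a 1.7-fold ratio has 99% power for lumefantrine, 93–94% for DHA and 88–89% for artemether. This stands and narrows the practical problem, but these effects are larger than the 35% that Section 9.4.1 claims.

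Fourth, the 1.7-fold effect is not stated for artemether or DHA, so their figures for it are illustrative. Finally, repeated measures, age control and population modelling may add precision. No gain is quantified, not every child will provide both regimens, and the test named in Section 9.4.2 is unpaired.

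**Conclusion.** The concern holds. The stated 80% power for a 35% AUC difference depends on a CV of 35–38% that Table 1 does not support for any of the three analytes it reports. At Table 1 variability, power for a 35% increase or raw-scale difference is roughly 20–49% after correction and at most 66% without it. That reading therefore fails whatever divisor is used.

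The consequence differs by analyte. Lumefantrine remains adequately powered for the anticipated 1.7-fold increase. The material weakness is artemether and DHA in the n=30 versus n=30 comparison of 5-day with 3-day AL in HIV-infected children.

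The result assumes log-normal AUCs, the sample sizes in the Table 1 column headers, similar variability in the new study, and a divisor of 3 where a correction is applied. It should be fixed, but it does not call the design or the enrolment target into question.

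**What to change.** In Section 9.4.1, replace the single CV with analyte-specific values from Table 1, or give the source of 35–38% and explain why it should be preferred to Table 1. State the Bonferroni divisor, the scale and the direction. If the divisor is 3, wording could be:

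> With n=30 per group and two-sided alpha 0.05/3, log-scale SDs of 0.52–0.54 (lumefantrine), 0.67 (DHA) and 0.72–0.74 (artemether) give 80% power for AUC ratios of about 1.56–1.59, 1.77–1.78 and 1.85–1.88 (reductions: 0.63–0.64, 0.56 and 0.53–0.54).

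The upper artemether value uses a footnoted control cell, so its n should be confirmed first. If the divisor is not 3, the ratios need recalculating.

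In Section 9.4.2, replace the unpaired t-test with an analysis of log AUC that accounts for repeated episodes within a child and adjusts for age, as Sections 9.4.1 and 9.1 already promise.

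The cost is protocol and SAP wording and a less favourable stated detectable difference. No added enrolment is needed.

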## 2.0 STUDY OBJECTIVES

### 2.1 Primary Objectives:

- 1) To evaluate and compare the PK exposure between 5-day AL treatment and 3-day al treatment in HIV-infected children on EFV-based ART
- 2) To evaluate and compare the PK exposure of 3-day and 5-day AL treatment in HIV-infected children on EFV-based ART to 3-day AL treatment in HIV-uninfected children not on ART.
- 3) To evaluate and compare the PK exposure of 3-day and 5-day AL treatment in HIV-uninfected children not on ART.
- 4) To evaluate the pharmacodynamics of AL in the context of extended dose regimens and HIV infection.

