### **6.7.4 Assays for artemether, DHA and lumefantrine**

Artemether, DHA and lumefantrine and active desbutyl-lumefantrine will be measured using optimized methods validated in our laboratory. All methods will utilize liquid chromatography tandem mass spectrometry.

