### 9.2 Outcome Measures

#### 9.2.1 Primary outcomes

- 1) Area under the plasma concentration versus time curve for all drug analytes.
- 2) Recurrent malaria following treatment by day 42 (recrudescence or new infection)

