**Table 8. Primary objectives and comparator groups for intensive PK study**

Primary Objectives	Comparison Groups
Impact of 5-day vs 3-day AL on AL exposure in HIV-infected children on EFV-based ART	HIV-infected children on EFV-based ART 3-day AL (n=30), vs. HIV-infected children on EFV-based ART 5-day AL(n=30).
Impact on AL exposure of 5-day AL in HIV-infected children on EFV-based ART vs 3-day AL in HIV-uninfected children	HIV-infected children on EFV-based ART 3-day AL (n=30), Vs. HIV-uninfected children 3-day AL (n=30, age 3-18years).
Impact of 5-day vs 3-day AL on AL exposure in HIV-uninfected children	HIV-uninfected children 5-day AL (n=50), vs. HIV-uninfected children 3-day AL (n=50).

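### The primary AUC outcome spans several analytes and contrasts, but the Bonferroni family is never defined and is absent from the analysis section, so the promised overall 0.05 is not secured and the 80% power cannot be verified

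*Combined protocol and SAP*

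**What the plan says.** Section 9.2.1 gives the first primary outcome as "Area under the plasma concentration versus time curve for all drug analytes". It names no lead analyte. Section 6.7.4 lists four measured compounds ("Artemether, DHA and lumefantrine and active desbutyl-lumefantrine will be measured using optimized methods"), although its title names three, and 9.4.2 defines an AUC for each of the four.

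Table 8 has three rows, each comparing two groups. Primary objective 2 (section 2.1) holds two comparisons, because it sets "3-day and 5-day AL treatment in HIV-infected children on EFV-based ART to 3-day AL treatment in HIV-uninfected children not on ART". The objectives therefore imply four contrasts. Row 2 of Table 8 also disagrees with itself: its objective column concerns the 5-day regimen in HIV-infected children, while its group column reads "HIV-infected children on EFV-based ART 3-day AL (n=30").

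On error and power, section 9.4.1 states "80% power to detect a difference in AUC of 35% or more" with 30 per group, "given an overall Type I error of 0.05, a Bonferroni correction for multiple comparisons", and the assumption that "the coefficient of variation (CV) for all AUC's is 35-38"%. It gives no number of comparisons, adjusted alpha, scale or direction.

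Section 9.4.2 says that parameters will be compared "using a two-sided unpaired t-test for two-group comparisons, and ANOVA for multi-group comparisons". It mentions no multiplicity adjustment and no order of testing.

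**The concern.** The design section promises a controlled overall error, and the analysis section describes tests at an unadjusted level. Neither says which tests form the family. With every analyte primary there are 9 to 16 AUC tests (3 or 4 analytes x 3 or 4 contrasts). A p-value between 0.05/12 = 0.0042 and 0.05 would count as significant under 9.4.2 but not under a 12-test Bonferroni correction.

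This matters because the analytes need not agree. Artemether and DHA are summarised over 8 or 24 hours, and lumefantrine to infinity. Hypotheses 1 and 3 claim superior PK exposure for the 5-day regimen. Without a family rule, that claim could rest on whichever analyte reaches 0.05. Section 3.1.1 says the comparisons are meant to inform treatment guidelines and policy.

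**Working it through.** **Inputs.** n = 30 per group, 35% difference, CV 35% to 38%, overall alpha 0.05 with Bonferroni (9.4.1); two-sided unpaired t-test (9.4.2). The number of tests m, the scale and the direction are not given, so each is varied.

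**Formula.** Power comes from the noncentral t with 58 df, alpha = 0.05/m and noncentrality = delta / (SD x sqrt(2/30)), where sqrt(2/30) = 0.2582.
- Raw scale, common SD: delta = 0.35, SD = CV, as fractions of the mean.
- Log scale: SD = sqrt(ln(1 + CV^2)), which is 0.340 at CV 35% and 0.367 at CV 38%; delta = ln 1.35 = 0.300 for an increase and -ln 0.65 = 0.431 for a decrease.

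**Reproducing the plan's 80%.** On the raw scale at CV 38%, noncentrality = 0.35 / (0.38 x 0.2582) = 3.57. With m = 6 (all pairwise comparisons of four groups, an inferred family) the critical value is 2.73 and power is 79.4%. So 80% is reachable from the plan's inputs, but only by supplying an m that the plan does not state.

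**Power at 30 v 30, CV 35% / 38%:**

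| m | Raw, 35% difference | Log, 35% increase | Log, 35% decrease |
|---|---|---|---|
| 3 | 91.7 / 86.1% | 82.6 / 75.6% | 99.2 / 97.9% |
| 4 | 89.8 / 83.5% | 79.6 / 72.0% | 98.9 / 97.3% |
| 6 | 86.8 / 79.4% | 75.1 / 66.7% | 98.3 / 96.1% |
| 9 | 83.4 / 75.0% | 70.3 / 61.3% | 97.6 / 94.7% |
| 12 | 80.8 / 71.7% | 66.7 / 57.4% | 96.9 / 93.5% |
| 16 | 78.0 / 68.4% | 63.1 / 53.6% | 96.1 / 92.1% |

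On the log scale at m = 12, the increase detectable with 80% power is 1.40-fold at CV 35% and 1.44-fold at CV 38%. The shortfall concerns the 30 v 30 contrasts. At 50 v 50 with m = 12 and CV 38%, power is about 95% on the raw scale and 87% for an increase on the log scale.

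**Family-wise error.** Simulated trials under a global null with shared arms (30/30/50/50; 30 controls in the contrast between HIV groups), 3 contrasts x 4 analytes. The correlation between analytes is an assumption: 0.5, range 0.8 to 0.3.
- No adjustment, as in 9.4.2: about 0.38 (0.28 to 0.42).
- Divisor 3, contrasts only: about 0.15 (0.11 to 0.16).
- Divisor 12: 0.03 to 0.05.

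For reference, 12 independent tests would give 1 - 0.95^12 = 0.46 unadjusted and 1 - (1 - 0.05/3)^12 = 0.18 with divisor 3.

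**The case against.** The strongest reply has four parts.

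- **The plan's figures are compatible.** A reader might infer that an overall 0.05 and 80% power contradict each other. The documents do not support that. On the raw scale both hold for three or four group contrasts, six comparisons give almost exactly 80% at CV 38%, and 9 or 12 tests keep it at CV 35%. Section 9.4.1 also speaks of a difference, not an increase, and a 35% decrease on the log scale keeps over 90% throughout. This stands.
- **The family may be group contrasts only.** Section 9.4.1 ties the correction to comparisons between groups, so that reading is natural, and correcting across a parent drug and its metabolite is a judgement. But 9.2.1 makes every analyte primary, and a contrasts-only divisor then leaves about 0.11 to 0.16, not 0.05.
- **The sections should be read together, and a global null is unrealistic.** Table 1 shows efavirenz/control AUC ratios of 0.30 to 0.48, so the contrast between HIV groups is unlikely to be null. This stands in part: 0.28 to 0.42 is the error rate of the literal rule, not a forecast. If only artemether and DHA are unaffected by the longer regimen, the chance of at least one false regimen claim on them is 17% unadjusted. That still exceeds 0.05.
- **ANOVA.** A reader might infer that a four-group ANOVA acts as a gate before the pairwise tests. No section says so, and every row of Table 8 is a two-group comparison. No part of this point rests on it.

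**Conclusion.** The point holds as a gap between the stated error control and the stated analysis. For the primary outcome as 9.2.1 defines it, 9.4.2 does not deliver an overall 0.05, and neither does a correction over contrasts alone. The error sizes rest on a global null and an assumed analyte correlation of 0.3 to 0.8. The 80% power is neither shown wrong nor verifiable. It holds for a small family on the raw scale, and falls to 72% to 81% (raw) or 57% to 67% (log, increase) at 12 tests.

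The practical weight for the expected regimen effect is limited. At the 1.7-fold increase anticipated in 9.5.1, power exceeds 99% even at 12 tests under the plan's CV. That reassurance depends on the CV. If the lumefantrine intervals in Table 1 are t-based 95% confidence intervals of geometric means, they imply a CV of 56% to 58%. For the controls, for example, the log SD is (ln 313 - ln 232) / 2 / 2.01 x sqrt(52) = 0.54. Power at 1.7-fold with divisor 12 would then be about 79% to 82%.

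**What to change.** 1. Reconcile row 2 of Table 8, where the objective and the group columns name different regimens, with primary objective 2. Then list the primary contrasts explicitly.
2. In 9.4.2, apply the Holm procedure at two-sided family-wise 0.05 to the listed pairwise tests. Either name lumefantrine AUC as lead analyte, make the other analytes secondary and run Holm over the contrasts, or run Holm over all contrasts x analytes. Holm controls the same error as Bonferroni and is never less powerful.
3. In 9.4.1, state the number of tests, the adjusted alpha, the scale and the direction. Restate the power or detectable difference for that family with its CV assumption beside it. With 12 tests on the log scale this would be about a 1.40- to 1.44-fold increase for 80% power, valid only if the CV is 35% to 38%.

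The cost is protocol and SAP wording, with no extra children or samples. The downside is a slightly less favourable stated detectable difference if the family spans analytes. Because the trial is open-label, the choice should be recorded before AUC results are compared by arm.
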